9.4.5 Pulse Oximetry

For the treatment-emergent oxygen saturation values by pulse oximetry, a summary of observed values and change from baseline values will be provided at each visit by treatment group.

The number and percentage of subjects with shift from baseline category (classified as normal/missing and low according to the reference range) to the category at the lowest percent of oxygen saturation during the TE period will be summarized by treatment group. The reference range for normal oxygen saturation is specified as >95%, and ≤95% for low oxygen saturation.

9.4.6 Ophthalmology Examination

Ophthalmology examination results will be provided in an individual subject data listing.

9.4.7 Physical Examination

Abnormal PE findings will be presented as an individual subject data listing only.

9.4.8 COVID-19 Impacted Visits

A listing containing subjects' visits impacted due to COVID-19 will be provided.

10 Interim and DMC Analyses

10.1 Interim Analysis

No interim analysis is planned at this moment; otherwise, SAP will be amended.

10.2 DMC analysis

The DMC's objectives and operational details have been defined in a separate document (DMC Charter) which was finalized before the first subject was screened in the study. The DMC's planned safety reviews of study data is outlined in the DMC Charter and DMC Statistical Analysis Plan.

12 LIST OF APPENDICES

Appendix A: Analysis Visit Windows for Safety and Efficacy Assessment

Table 12-1 Analysis Visit Windows for Safety and Efficacy Assessments			
Assessment	Visit¹	Target Study Day	Analysis Visit Window (in study days)^{2, 3, 4, 5}
Safety Assessment			
Serum Chemistry Hematology	Day 1 (Baseline)	1	≤1 Pre-dose
	Day 15	15	[1, 22]
	Week 4	29	(22, 43]
	Week 8	57	(43, 85]
	Week 16	113	(85, 141]
	Week 24	169	(141, 183]
	Safety Follow-up	Not applicable	Use nominal visit
Standard 12-lead ECG	Day 1 (Baseline)	1	≤1 Pre-dose
	Week 8	57	[1, 85]
	Week 16	113	(85, 141]
	Week 24	169	(141, 183]
	Safety Follow-up	Not applicable	Use nominal visit
Vital signs (excluding BMI, Weight and Height, and their z-scores) and pulse oximetry	Day 1 (Baseline)	1	≤1
	Day 15	15	[1, 22]
	Week 4	29	(22, 43]
	Week 8	57	(43, 85]
	Week 16	113	(85, 141]
	Week 24	169	(141, 183]
	Safety Follow-up	Not applicable	Use nominal visit
Coagulation	Day 1 (Baseline)	1	≤1 Pre-dose
	Week 24	169	[1, 183]
BMI, Weight, Height and the corresponding z-scores	Day 1 (Baseline)	1	≤1
	Day 15	15	(1, 22]
	Week 4	29	(22, 43]
	Week 8	57	(43, 85]
	Week 16	113	(85, 141]
	Week 24	169	(141, 183]
	Safety Follow-up	Not applicable	>183
Efficacy Assessment and Pharmacodynamic Assessment			

Table 12-1 Analysis Visit Windows for Safety and Efficacy Assessments			
Assessment	Visit¹	Target Study Day	Analysis Visit Window (in study days)^{2, 3, 4, 5}
Sweat Chloride Lung Clearance Index (LCI)	Day 1 (Baseline)	1	≤1 Pre-dose
	Day 15	15	(1, 22]
	Week 4	29	(22, 43]
	Week 8	57	(43, 85]
	Week 16	113	(85, 141]
	Week 24	169	(141, 183]

¹ Visit name for analysis purpose is used to report data in tables and figures.

² The analysis visit windows will be applied using the following rules for both scheduled and unscheduled visits:

- a. If no numerical measurement is available within a visit window, the measurement will be considered missing for the visit.
- b. If there is more than 1 numerical measurement available within a visit window, use the following rules:
 - i. The measurement closest to the target day will be used; or
 - ii. If there are multiple measurements with the same distance from the target day, the latest measurement will be used. If the latest measurement cannot be determined, then unscheduled visit will be selected

³ For measurements collected on the date of first dose of study drug, if it cannot be determined whether the measurement is before or after the first dose:

- a. Scheduled measurement will be treated as pre-dose observation.
- b. Unscheduled measurement will be treated as post-dose observation.

⁴ For safety assessment, Safety Follow-up analysis visit will be based on nominal Safety Follow-up visit. If a subject doesn't have a nominal Safety Follow-up visit but has an ETT visit with study day >183, then the ETT visit will be mapped into Safety Follow-up analysis visit.

⁵ For efficacy assessments and nutrition variables (BMI, Weight, Height and their Z-scores), if there are multiple assessments >183, then nominal Safety Follow-up visit will be mapped to Safety Follow-up visit. If there is only ETT assessment > 183, the ETT visit will be mapped to the Safety Follow-up visit; else if there are multiple assessments with >183 then select the earliest record.

Derived Variables:

1. Age (in years) at first dose date and nominal visit (for demographics, listing and the calculation of [percent] predicted spirometry variables):

Obtain the age at informed consent (in days) in “yy, mm” format (e.g., 24 years, 6 months) from the Vital Signs (VS) page at the Screening Visit, and add 0.5 month to convert to days.

Obtain the informed consent date.

Then age (in years) at first dose or nominal visit = [(first dose date or nominal visit date – informed consent date) in days + age at informed consent (in days)]/365.25.

Table 12-1 Analysis Visit Windows for Safety and Efficacy Assessments			
Assessment	Visit¹	Target Study Day	Analysis Visit Window (in study days)^{2, 3, 4, 5}
2.	Age (in months) at nominal visit (for use in calculation of BMI, height and weight z-score):		
	Obtain the age at informed consent (in months) in “yy, mm” format (e.g., 24 years, 6 months) from Vital Signs (VS) page at the Screening Visit.		
	Obtain the informed consent date.		
	Then age (in months) at nominal visit = integer part of $\{[(\text{age at informed consent (in months)} + 0.5 + \text{diff}(\text{first dose date or nominal visit date, informed consent date}) \text{ in months})] + 0.5$.		
3.	Missing first dose date or last dose date		
	If the first dose date is missing, use Day 1 visit date to impute.		
	If the last dose date is missing or partial date is reported, the last dose date will be imputed based on, in descending order priority, the Early Treatment Termination (ETT) visit date, last visit date before the Safety Follow-up, or the last study drug administration date from EX SDTM domain, as appropriate. The imputation algorithm will ensure the imputed last dose date does not exceed the study participation end date.		
4.	Sweat Chloride:		
	Non-missing sweat chloride concentrations from the left arm and right arm with assessment end date/time for a given arm up to 30 minutes after first dose time in treatment period will be considered for baseline.		
5.	Electrocardiogram:		
	Baseline is defined as the most recent pretreatment measurement before the first dose of study drug in the Treatment Period. If multiple ECG measurements are obtained on the same calendar day during the TE period,		
	
 ○ For summary purpose, the calculated average ECG will be used as the ECG value on that day; ○ For threshold analysis purpose, all reported ECG values will be used. 		

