Event/ Assessment ^a	Day 1 ^b	Day 3 ± 1 day	Day 15 ± 3 days	Week 4 ± 5 days	Week 8 ± 5 days	Week 12 ± 5 days	Week 16 ± 5 days	Week 20 ± 5 days	Week 24 ± 5 days	ETT Visit	Safety Follow-up ^c 28 (± 7) Days After Last Dose of Study Drug	Comments
Clinic Visit	X		X	X	X		X		X	X	X	
Telephone contact		X				X		X				Assess subject's status, any AEs, concomitant medications, treatments, and procedures.
Inclusion/ exclusion criteria review	X											Section 8
Randomization	X											Randomization may occur on either Day - 1 or Day 1, after all eligibility criteria are confirmed.
Safety and Efficacy Assessments												
Ophthalmologic examination									X at or up to 4 weeks before	X		Section 11.5.5
Height and weight	X		X	X	X		X		X	X	X	Measured before study drug dosing with shoes off

^a All assessments will be performed before dosing unless noted otherwise.

^b To enter the Treatment Period, conditions for entry must be satisfied.

^c The Safety Follow-up Visit is not required for subjects who complete the Week 24 Visit and enroll in an optional open-label extension safety study within 28 days after the last dose of study drug (Section 9.1.3).

Table 3-2 Study VX19-445-116: Treatment Period and Safety Follow-up Visit

Event/ Assessment ^a	Day 1 ^b	Day 3 ± 1 day	Day 15 ± 3 days	Week 4 ± 5 days	Week 8 ± 5 days	Week 12 ± 5 days	Week 16 ± 5 days	Week 20 ± 5 days	Week 24 ± 5 days	ETT Visit	Safety Follow-up ^c 28 (± 7) Days After Last Dose of Study Drug	Comments
Vital signs and pulse oximetry	X		X	X	X		X		X	X	X	Performed after subject has been at rest for at least 5 minutes (Section 11.5.3)
Physical examination	X								X	X		Symptom directed physical examinations may be performed at any time if deemed necessary by the investigator (Section 11.5.3)
Standard 12-lead ECG	X				X		X		X	X	X	Performed prior to any procedure that may affect heart rate (e.g., blood draws) and after subject has been at rest for at least 5 minutes (Section 11.5.4)

Table 3-2 Study VX19-445-116: Treatment Period and Safety Follow-up Visit

Event/ Assessment ^a	Day 1 ^b	Day 3 ± 1 day	Day 15 ± 3 days	Week 4 ± 5 days	Week 8 ± 5 days	Week 12 ± 5 days	Week 16 ± 5 days	Week 20 ± 5 days	Week 24 ± 5 days	ETT Visit	Safety Follow-up ^c 28 (± 7) Days After Last Dose of Study Drug	Comments
Sweat chloride	X		X	X	X		X		X	X		
Multiple-breath washout	X		X	X	X		X		X	X		Performed in multiple replicates, pre-bronchodilator, before the AM dose, and before spirometry assessment (Section 11.3.1).

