11.5.3 Physical Examinations and Vital Signs

A PE of all body systems and vital signs assessment will be performed at screening and select study visits (see Table 3-1 and Table 3-2). At other visits, symptom-directed PEs and symptom-directed vital signs assessments can be performed at the discretion of the investigator or healthcare provider.

A PE includes a review of the following systems: head, neck, and thyroid; eyes, ears, nose, and throat (EENT); respiratory; cardiovascular; lymph nodes; abdomen; skin; musculoskeletal; and neurological. Breast, anorectal, and genital examinations will be performed when medically indicated. After screening, any clinically significant abnormal findings in PEs will be reported as AEs.

Symptom-directed PEs and symptom-directed vital signs assessment may be performed if appropriate.

Vital signs include blood pressure (systolic and diastolic), temperature, pulse rate, and respiration rate. The subject will be instructed to rest for at least 5 minutes before vital signs are assessed.

Arterial oxygen saturation by pulse oximetry will be assessed following at least a 5-minute rest and before study drug dosing. At visits when study drug is taken at the site, pulse oximetry will be collected before study drug dosing.

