12.3 Statistical Analysis

12.3.1 General Considerations

Continuous variables will be summarized using the following descriptive summary statistics: number of subjects (n), mean, SD, median, minimum value (min), and maximum value (max).

Categorical variables will be summarized using counts and percentages.

Treatment-emergent (TE) period will include the time from the first dose of study drug in the Treatment Period (ELX/TEZ/IVA or placebo) through 28 days after the last dose or the completion of study participation date (as defined in Section 9.1.6), whichever occurs first.

Baseline unless otherwise specified, will be defined as the most recent non-missing measurement (scheduled or unscheduled) collected before the first dose of study drug. For ECG, baseline will be defined as the most recent pretreatment measurement, or the average of triplicate measurements if the most recent pretreatment measurement is obtained in triplicate, before the first dose of study drug.

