9 STATISTICAL ANALYSIS

9.1 General Considerations

Continuous variables will be summarized using the following descriptive summary statistics: the number of subjects (n), mean, SD, median, minimum value (min), and maximum value (max).

Categorical variables will be summarized using counts and percentages.

Baseline value, unless otherwise specified, will be defined as the most recent non-missing measurement (scheduled or unscheduled) collected before the first dose of study drug in the Treatment Period.

Absolute change from baseline will be calculated as post-baseline value – baseline value.

Relative change from baseline will be calculated as (post-baseline value – baseline value)/baseline value.

Treatment-emergent (TE) Period will include the time from the first dose date of study drug to 28 days after the last dose of the study drug or to the date of completion of study participation, whichever occurs first.

Unscheduled visits: Unscheduled visit measurements will be included in analysis as follows:

- 1) In scheduled visit windows per specified visit windowing rules
- 2) In the derivation of baseline and last on-treatment measurements
- 3) In the derivation of maximum and minimum values during TE period, and maximum and minimum change from baseline values during TE period for safety analyses
- 4) In individual subject data listings as appropriate

Visit windowing rules: The analysis visit windows for protocol-defined visits are provided in [Appendix A](#).

Incomplete/missing data will not be imputed, unless specified otherwise.

Outliers: No formal statistical analyses will be performed to detect or remedy the presence of statistical outliers, unless specified otherwise.

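### SAP 9.1 starts the treatment-emergent period on the first dose date and the vital-sign and oximetry windows overlap on Day 1, so a pre-dose reading is both baseline and treatment-emergent

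*SAP*

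**What the plan says.** **Windows.** In SAP Appendix A, Table 12-1, the row "Vital signs (excluding BMI, Weight and Height, and their z-scores) and pulse oximetry" has a Day 1 (Baseline) window of `≤1` and a Day 15 window of `[1, 22]`. Neither cell says pre-dose or post-dose. Where several values fall in one window, "The measurement closest to the target day will be used". Footnote 3 covers values from the first dose date whose order relative to dosing is unknown: scheduled ones are treated as pre-dose, unscheduled ones as post-dose.

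**TE period.** SAP 9.1: "Treatment-emergent (TE) Period will include the time from the first dose date of study drug to 28 days after the last dose" (or to completion of participation, if earlier). Protocol 12.3.1: "Treatment-emergent (TE) period will include the time from the first dose of study drug in the Treatment Period". The SAP starts from a date, the protocol from an event.

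**Timing on Day 1.** Protocol Table 3-2, note a: "All assessments will be performed before dosing unless noted otherwise". Protocol 11.5.3 adds that oximetry is done after rest and "before study drug dosing. At visits when study drug is taken at the site, pulse oximetry will be collected before study drug dosing". SAP 9.1 takes baseline as the last available value before the first dose.

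**Outputs that use the TE period.** The oximetry table in SAP 9.4.5 goes from the baseline category "to the category at the lowest percent of oxygen saturation during the TE period", with 95% or below classed as low. SAP 9.4.4 counts subjects who meet a vital-sign threshold at any time in the TE period. The limits are in Table 12-5, for example systolic pressure above 120 mmHg or diastolic above 80 mmHg.

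**The concern.** Treatment-emergent outputs should describe what happens after dosing starts. If the pre-dose Day 1 reading sits inside the TE period, the baseline is one of the values from which the TE minimum, maximum and threshold flags are derived. The comparison is then partly of baseline with itself.

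Vital signs and pulse oximetry are named in the secondary safety endpoint. At stake are one cell of the saturation shift table, the threshold counts in both arms, and, for a few subjects at most, the Day 15 by-visit summary. No hypothesis test is involved.

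**Working it through.** The plan states no figure on this point, so the check is of definitions, followed by an illustration on assumed inputs.

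**1. Is Study Day 1 in both windows?**

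| Table 12-1 row | Baseline | First post-baseline window | Day 1 in both? |
|---|---|---|---|
| Chemistry, hematology | `≤1` Pre-dose | `[1, 22]` | Yes |
| ECG | `≤1` Pre-dose | `[1, 85]` | Yes |
| Vital signs, oximetry | `≤1` | `[1, 22]` | Yes |
| Coagulation | `≤1` Pre-dose | `[1, 183]` | Yes |
| BMI, weight, height | `≤1` | `(1, 22]` | No |
| Sweat chloride, LCI | `≤1` Pre-dose | `(1, 22]` | No |

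The vital-sign row is the only one with both an unlabelled baseline cell and a post-baseline window closed at Day 1. In the other three overlapping rows the baseline cell is labelled, but nothing restricts the post-baseline window to post-dose values.

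**2. Is a pre-dose Day 1 reading in the TE period?** It falls on the first dose date, so it is inside under SAP 9.1. It precedes the first dose, so it is outside under Protocol 12.3.1. Footnote 3 labels values of unknown order; it removes nothing from a window or from the TE period.

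**3. When does the Day 1 reading become the Day 15 result?** Its distance from the target is |1 − 15| = 14 days. The largest distance for Days 2 to 22 is |2 − 15| = 13. Any later value in the window therefore wins, and the Day 1 reading is used only if there is none. That subject's change is then exactly 0. If a share m of subjects is filled in this way, the mean change is (1 − m) times the mean among the rest. The documents give no value for m.

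**4. Saturation shift.** Let b be the Day 1 baseline and p the lowest later TE value. As written, the table uses min(b, p), which cannot exceed b.

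- b ≤ 95: min(b, p) ≤ 95 always, so the low-to-normal cell is empty for these subjects whatever happens on treatment.
- b > 95: min(b, p) ≤ 95 exactly when p ≤ 95, so the normal-to-low cell is unchanged. This assumes one pre-dose reading on Day 1, as scheduled.
- Baseline carried from screening because Day 1 is missing: no effect.

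**5. Thresholds.** A Day 1 baseline beyond an absolute limit is counted as treatment-emergent. Criteria that require a change from baseline, such as the 5% weight criteria, are not triggered, because the change of baseline from itself is 0.

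**6. Rough size, on assumptions that are not in the documents.** Saturation was simulated with one baseline and five later readings, no treatment effect, rounding to whole percent and a cap of 100.

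| Mean, SD, within-subject correlation | Low at baseline | Low-to-normal among these, Day 1 excluded | Same, Day 1 included | Lowest value ≤95%: excluded → included |
|---|---|---|---|---|
| 97.5, 1.3, 0.3 | 6.1% | 49.5% | 0% | 23.2% → 26.2% |
| 97.5, 1.3, 0.6 | 6.2% | 28.9% | 0% | 18.1% → 19.9% |
| 98, 1.2, 0.5 | 1.9% | 53.6% | 0% | 7.0% → 8.0% |
| 97, 1.5, 0.5 | 15.8% | 21.4% | 0% | 41.3% → 44.7% |

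The rise in the last column is the product of the second and third, for example 0.061 × 0.495 = 0.030. Across the four rows it is 1.0 to 3.4 percentage points. With the planned 54 per arm that is 0.010 × 54 ≈ 0.5 to 0.034 × 54 ≈ 1.8 subjects per arm.

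**The case against.** The strongest reply is that the plan, read as a whole, does not intend double use. Baseline is defined as pre-dose, the protocol starts the TE period at the first dose, and footnote 3 sorts Day 1 values into pre-dose and post-dose, which has a purpose only if the two go to different places. A programmer might well exclude pre-dose values by convention. This stands as evidence of intent, but the convention is not written down, and the SAP and protocol give different starting points.

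Four further objections stand in full:

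- The vital-sign row is not the sole problem. Three other rows have post-baseline windows closed at Day 1, and the date-based start covers every TE output.
- The shift and threshold effects come from SAP 9.1. Editing the row alone would leave them in place.
- A table of the lowest saturation is built to show deterioration, and the normal-to-low cell is intact.
- Starting the TE period at a clock time throughout would disturb rules that work by date. Protocol 13.1.1.3 records the date of an adverse event, SAP 9.4.1 defines TEAEs from the first dose date, Appendix D imputes missing starts to that date, and Table 12-2 classifies medications by date.

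**Conclusion.** The point holds on the literal text and is of low severity. A pre-dose Day 1 reading is baseline and also falls in the SAP's TE period. The empty low-to-normal cell for subjects with a low Day 1 baseline follows by logic and rests on no assumed rate. Pre-dose readings beyond an absolute threshold are counted as treatment-emergent in both arms. How many subjects are affected cannot be learned from the documents; the simulated figures show direction and rough scale only.

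A reader might infer more than the documents support:

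- *That worsening on drug is hidden.* It is not: normal-to-low shifts are unchanged with the single scheduled Day 1 reading.
- *That Day 15 changes are materially diluted.* This needs subjects with no value on Days 2 to 22. The 10% dropout in Protocol 12.1 is an assumption for the whole Treatment Period, not for the first three weeks, and the COVID-19 addendum allows vital signs and oximetry at home.
- *That the efficacy result is at risk.* The LCI and sweat chloride row labels baseline as pre-dose and opens Day 15 after Day 1, and the safety outputs are descriptive.

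**What to change.** 1. **SAP 9.1.** Keep the date-based TE period for adverse events and medications. Add one sentence: measurements taken before the first dose on Day 1, or treated as pre-dose under Table 12-1 footnote 3, are baseline only and are excluded from post-baseline visit windows and from TE minimum, maximum, threshold and shift derivations. This also covers chemistry, hematology, ECG and coagulation.
2. **Table 12-1.** Label the vital-sign and oximetry baseline cell `≤1` Pre-dose. This also keeps a post-dose Day 1 reading out of the baseline window. State that windows opening at `[1` take post-dose values only, or use `(1, 22]` for this row as the LCI row does.

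The cost is one sentence and a few table labels before database lock, with no new data. If `(1, 22]` is chosen, a post-dose Day 1 vital sign drops out of the Day 15 by-visit summary but stays in the TE threshold and shift tables. The post-dose-only reading avoids even that.
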